12.3.1. Donning/doffing the device

12.3.2. Standing/sitting

Protocol Name:	Investigational Study of the Ekso Bionics Powered Exoskeleton for High-Dosage Use by Individuals with Spinal Cord Injury in a Non-Clinical Environment
Principal Investigator:	[name], Sr. Controls Engineer
Primary Contact Name/Contact Info:	[name], Sr. Controls Engineer [contact] [contact]
Date Revised:	9/28/2015
Study Number:	13098-01

- 12.3.3. Walking
- 12.3.4. Balance and stability
- 12.3.5. Maneuverability
- 12.3.6. Duration of sessions
- 12.3.7. Device reliability
- 12.3.8. Physical and psychological deviations
- 12.3.9. Human factors and usability

13. Cost and Compensation

13.1. Equitable access plan:

There is a substantial cost to enrolling a subject in the study. The costs fall into four categories:

1. Training cost
2. Testing costs
3. Subject/Spotter costs
4. Device cost

Ekso will entirely bear the training cost (1) and cost associated with data acquisition (e.g. Dexa scan) (2). The subject will be responsible for the potential cost of obtaining a medical release from their physician. The subject will also be responsible for providing a spotter since this will often be an unpaid family member and therefore have no associated cost (3). The Ekso device (\$130,000-160,000 retail depending on features) is a substantial cost which some subjects will not be able to pay, nor can Ekso afford to provide enough devices for the desired number of subjects (4). Since Ekso Bionics' objective is to study the objectives in Section 3, the device will be equally accessible to all qualified subjects at cost. This will be achieved by one of the following options.

Protocol Name:	Investigational Study of the Ekso Bionics Powered Exoskeleton for High-Dosage Use by Individuals with Spinal Cord Injury in a Non-Clinical Environment
Principal Investigator:	[name], Sr. Controls Engineer
Primary Contact Name/Contact Info:	[name], Sr. Controls Engineer [contact] [contact]
Date Revised:	9/28/2015
Study Number:	13098-01

13.1.1. Subjects may purchase their own Ekso device which they may then keep at the end of the study. This will enable a prompt start to their participation in the study.

13.1.2. Ekso will introduce subjects to non-profit organizations specifically available to fund robotic medical devices. These organizations include but are not limited to the Bridging Bionics Foundation

(<https://www.facebook.com/bridgingbionics?ref=stream>,
<https://twitter.com/bridgingbionics>) and SoldierSocks
http://www.facebook.com/pages/Soldier-Socks/147478454297?ref=stream&hc_location=timeline).

SoldierSocks has already committed to donating ten Ekso devices to veterans of war (Appendix E).

13.1.3. Ekso Bionics will assist the subject to establish a fundraising program under the Ekso Hope program (<http://www.eksobionics.com/eksohope>). Ekso Hope has successfully raised hundreds of thousands of dollars to enable the purchase Ekso devices. The foundation set up a program and assist individuals reach their goal.

14. Data Management and Confidentiality

14.1. Data may be collected manually, on video, on a computer embedded in the device or transferred to an Ekso Bionics computer.

14.2. The subject will be assigned an ID number so Ekso Bionics can keep all of the data collected during the duration of the study. Only the subject's ID number will be associated with the test session, not the subject's name. Only the Investigators will have access to the subject's identifying name and number. The identifying information will be kept in 1) a secure, password protected computer file on a server and 2) hard copies stored in

Protocol Name:	Investigational Study of the Ekso Bionics Powered Exoskeleton for High-Dosage Use by Individuals with Spinal Cord Injury in a Non-Clinical Environment
Principal Investigator:	[name], Sr. Controls Engineer
Primary Contact Name/Contact Info:	[name], Sr. Controls Engineer [contact] [contact]
Date Revised:	9/28/2015
Study Number:	13098-01

a locked cabinet located at the Ekso Bionics facility in Richmond, CA.

14.3. Data obtain remotely from the device will include but is not limited to number of steps taken during the session, the total distance travelled, the distance between steps, the force on various device components including pressure and torque, the location of the subject in relation to the device to evaluate balance and stability.

14.4. Physiological and psychological data will be gathered per Section 6.1.

14.5. Data will be stored for ten years.

14.6. An authorized Ekso Bionics staff member will transfer the data to the Ekso Bionics server at least once during the duration of the study. Data will be cleared from the device upon transfer; although, a portion of the data can be reviewed by the subject on the Ekso Pulse website. Ekso Pulse is a website designed specifically for users to review the data associated with their walking sessions. The Ekso Pulse site is protected by a user specific login. The server is under the same security measures as the primary Ekso server.

14.7. Data security and subject privacy measures will be taught at clinical training sessions to all clinicians, engineers or any Ekso Bionics staff responsible for testing and capturing data. Ekso Investigators will agree upon a secure password, file location and locked cabinet prior to the start of any testing. Keys to the cabinet will be in the sole, personal possession of the Investigators.

14.8. The data are intended to guide the development of the Ekso device for home use and to analyze the clinical effect on the subjects. Much of the analysis will be subjective in nature where the researchers will ignore outliers and be able visually

Protocol Name:	Investigational Study of the Ekso Bionics Powered Exoskeleton for High-Dosage Use by Individuals with Spinal Cord Injury in a Non-Clinical Environment
Principal Investigator:	[name], Sr. Controls Engineer
Primary Contact Name/Contact Info:	[name], Sr. Controls Engineer [contact] [contact]
Date Revised:	9/28/2015
Study Number:	13098-01

verify the data quality. Any suspicious data will be ignored or verified by comparing it with the videos and pictures.

14.9. The computer data, video and written notes will be evaluated and analyzed based on the needs of the Ekso Bionics engineering, marketing and business requirements. Analysis may include observation, statistical deviation, or other methods to enable results.

14.10. Written data, including subject questionnaires, will be given to study personnel at each checkup. This data will be transferred to the principal investigator by physical handoff or certified mail where physical handoff is not possible.

15. Provisions to Monitor the Data to Ensure the Safety of Subjects

15.1. This study does not require a Data and Safety Monitoring Committee or Board. This is a pilot study. It is considered an intervention, behavioral, learning-based training study with minimal risk to subjects.

16. Risks to Participants

16.1. The risk of falling: This could be caused by loss of control of the ambulation activity by the participant or spotter as well as malfunction of the Ekso device itself. The risk of falling will be minimized by having a trained spotter with the subject at all times. The risk of falling is further mitigated by allowing only very experienced subjects who have been approved by the Ekso Bionics Clinical Team walk in the device during the study. This risk is similar to any gait therapy in which subjects with lower extremity disorders are standing and walking.

16.2. Risk of exceeding subject range of motion: This would be caused if the Ekso moved the subject beyond their normal range of

Protocol Name:	Investigational Study of the Ekso Bionics Powered Exoskeleton for High-Dosage Use by Individuals with Spinal Cord Injury in a Non-Clinical Environment
Principal Investigator:	[name], Sr. Controls Engineer
Primary Contact Name/Contact Info:	[name], Sr. Controls Engineer [contact] [contact]
Date Revised:	9/28/2015
Study Number:	13098-01

motion, resulting in a strain, sprain and/or fracture. This risk is mitigated by mechanical hard stops that prevent the device from exceeding a normal human range of motion even in the event of a failure in the electrical or software systems. Software systems are also in place to further reduce range of motion to improve fit and comfort for subjects during walking. Subjects will be evaluated by trained Ekso Bionics clinicians who will eliminate any subjects from participation if they cannot meet the required range of motion.

16.3. Discomfort, skin pressure/friction, bruising, pain, or unusual swelling caused by the exoskeleton which has the potential to lead to skin breakdown or abrasions. All locations where the subject contacts the exoskeleton are padded to prevent bruising or skin irritations. Also all pinch points are covered and protected from catching either skin or clothing. Adjustments to the harness placement and additional padding will be assessed to decrease the risk of skin breakdown as well.

16.4. Blood pressure instability during use of the device related to standing or activity as well as reflex bowel or bladder activity or autonomic instability during use of the device. This risk will be reduced with frequent assessment of subject's symptoms as well as assessment of blood pressure, heart rate, and oxygen saturation during initial device training by research physical therapists. Activity will be stopped in the event of instability of vital signs and as recognized by experienced research personnel. Spotters will be trained to recognize signs and symptoms associated with blood pressure instability and to stop activity if present.

16.5. Spasms triggered by joint movement in the device. This risk will be reduced through screening prior to enrollment in the study with exclusion of subjects with severe spasticity.

Protocol Name:	Investigational Study of the Ekso Bionics Powered Exoskeleton for High-Dosage Use by Individuals with Spinal Cord Injury in a Non-Clinical Environment
Principal Investigator:	[name], Sr. Controls Engineer
Primary Contact Name/Contact Info:	[name], Sr. Controls Engineer [contact] [contact]
Date Revised:	9/28/2015
Study Number:	13098-01

16.6. There is a risk of device malfunction causing injury from falling or unintended motion of Ekso. Testing the device with Ekso Bionics employees without disability prior to a subject wearing the device will minimize risk of malfunction of the Ekso. Device malfunction is also mitigated through numerous safety features of the device. Redundant position sensing on all of the actuated joints ensures that the motors are always controlled using reliable sensor information. If the redundant sensors ever do not agree then the device shuts down. An emergency disable button is always available to the spotter to instantly shut down the device. This is implemented via hardware, so it is effective even during a software malfunction. The device is equipped with fail-safe brakes on the actuated knee joints, so if the device loses power or is shut down for any reason the knees will continue to support the subject. Finally there are numerous sensor, motor, and software monitoring systems in place. If any abnormality is detected (such as excess joint speed or force) the software shuts down the device in a safe manner.

16.7. The risk of fractures with use of the device: this will be minimized by requiring medical clearance for all participants and requiring all participants to be actively involved in a standing program.

16.8. The risk of musculoskeletal injury for the spotter: This could be caused by an attempt to correct a significant loss of balance during ambulation by the Ekso user as well as malfunction of the Ekso device itself causing a need for additional support to prevent a fall from occurring. The risk of musculoskeletal injury may also occur when lifting and moving the device. This risk will be minimized by providing the spotter with training related to safe body-mechanics during all aspects of device use. The risk of musculoskeletal injury for the spotter is further

Protocol Name:	Investigational Study of the Ekso Bionics Powered Exoskeleton for High-Dosage Use by Individuals with Spinal Cord Injury in a Non-Clinical Environment
Principal Investigator:	[name], Sr. Controls Engineer
Primary Contact Name/Contact Info:	[name], Sr. Controls Engineer [contact] [contact]
Date Revised:	9/28/2015
Study Number:	13098-01

mitigated by allowing only experienced subjects who have been approved by the Ekso Bionics Clinical Team walk in the device during the study.

16.9. The use of the Ekso system may involve risks that are currently unforeseeable as this is a trial to assess safety and efficacy of the Ekso device.

17. Provisions for Research Related Harm/Injury

17.1. If medical resources are required, the identified spotter must immediately contact appropriate medical services or call 911. Ekso Bionics principal investigator should also be contacted as soon as the subject is medically stable. For minor injuries, a local hospital emergency room will be identified as part of an emergency plan established prior to allowing use of the device.

17.2. This device has been determined to be NSR (non-significant risk) by Ekso Bionics due to the spotting requirement.

18. Potential Benefits to Subjects

18.1. There may be no direct benefit to the participants. The main benefit of this study is to determine the progression of technology to enhance functional ambulation, improved health and independence of people with spinal cord injuries. The feedback obtained from the participants and therapists will provide insights to the company for the next iteration of the design of the Ekso device.

19. Provisions to Protect the Privacy Interests of Subjects

19.1. Each participant will be assigned a coded identification number to designate all evaluations. Data will be stored by the coded identification number without information identifying the individual. All data, written and electronic, will be stored on

Protocol Name:	Investigational Study of the Ekso Bionics Powered Exoskeleton for High-Dosage Use by Individuals with Spinal Cord Injury in a Non-Clinical Environment
Principal Investigator:	[name], Sr. Controls Engineer
Primary Contact Name/Contact Info:	[name], Sr. Controls Engineer [contact] [contact]
Date Revised:	9/28/2015
Study Number:	13098-01

the Ekso Bionics server with password protection. Data will only be available to the researchers involved in the studies.

20. Payments to Subjects

No payments will be provided.

21. Consent Process

21.1. Ekso Bionics will require all participants to sign an Ekso Bionics Medical Release/Consent Form and Permission to Obtain Medical Treatment prior to the preliminary evaluation. Spotters will be required to sign an Ekso Bionics Consent Form:

21.1.1. All consent information will be provided to the subject in advance of their clinical screening.

21.2. There will be no waiting period required between the subjects being informed of risks and their providing of consent for participation in the study. Payment for the device must be received in most cases prior to starting the study.

22. Informed Consent Process for Research

22.1. The consent process will be directly conducted by a member of the Ekso Bionics clinical team who is under the direct supervision of [name], Ekso Bionics' Clinical Director. The consent process typically takes 30-60 minutes for the subject to understand and consent to participate in the study.

22.2. Only test subjects capable of comprehending and acknowledging the consent form will be included in the test.

	Protocol Name:	Investigational Study of the Ekso Bionics Powered Exoskeleton for High-Dosage Use by Individuals with Spinal Cord Injury in a Non-Clinical Environment
	Principal Investigator:	[name], Sr. Controls Engineer
	Primary Contact Name/Contact Info:	[name], Sr. Controls Engineer [contact] [contact]
	Date Revised:	9/28/2015
	Study Number:	13098-01

Appendices

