6.1.4. Duration of training session in each walking mode (FirstStep, ActiveStep, ProStep)

6.1.5. Perceived rate of exertion (PRE) - Borg Perceived Rate of Exertion Scale

6.1.6. Bowel function - Modified International SCI Bowel Function Basic Data Set

6.1.7. Bladder function - Modified International SCI Lower Urinary Tract Basic Data Set

6.1.8. Frequency of secondary health conditions (urinary tract infections, pressure ulcerations, respiratory conditions)

6.1.9. Quality of life (QOL) - International SCI Quality of Life Basic Data Set

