Primary Contact Name/Contact Info:	[name], Sr. Controls Engineer [contact] [contact]
Date Revised:	9/28/2015
Study Number:	13098-01

6.4.9. Helping the subject safely perform simple daily tasks inaccessible to the subject while in the device (e.g., bend down to get a plate from a cabinet or open a door)

6.5. Ekso Bionics will:

6.5.1. Evaluate the efficacy of a spotter in a home environment.
6.5.2. Evaluate the safety of using the device in a home environment.

6.6. After initial training at either Ekso Bionics or at the participant's home, a follow-up evaluation device operation may be conducted either in-person or by video at weeks 3 and 7. Review meetings will be held every three months from the time the device is delivered to the subject's home (or more frequently) to evaluate safety and efficacy. Information gathered from the study and status meetings will be used by Ekso Bionics to further the product development. Information may also be used by Ekso Bionics Marketing to determine the most appropriate market for the device and by Clinicians to aid in training future clinical staff.

Schedule of study measure.

	Baseline	3 months	6 months	9 months	12 months	Every 6 months after
Device measures (6.1.1 – 6.1.4)		✓	✓	✓	✓	✓
Physiological measures (6.1.5 – 6.1.7)	✓	✓	✓	✓	✓	✓
Frequency of secondary health conditions (6.1.8)	✓	✓	✓	✓	✓	✓

	Protocol Name:	Investigational Study of the Ekso Bionics Powered Exoskeleton for High-Dosage Use by Individuals with Spinal Cord Injury in a Non-Clinical Environment				
	Principal Investigator:	[name], Sr. Controls Engineer				
	Primary Contact Name/Contact Info:	[name], Sr. Controls Engineer [contact] [contact]				
	Date Revised:	9/28/2015				
	Study Number:	13098-01				

Quality of Life measures (6.1.9)	√	√	√	√	√	√
Functional ability (6.1.10)	√	√	√	√	√	√
Pain (6.1.11)	√	√	√	√	√	√
Spasticity (6.1.12)	√	√	√	√	√	√
Strength testing (6.1.13)	√	√	√	√	√	√
Bone Density (6.1.14)	√				√	

7. Inclusion and Exclusion Criteria

7.1. Subject Inclusion Criteria:

Participants must have a spinal cord injury between C7-L3 resulting in motor paralysis.

Participants must meet each of the remaining criteria:

7.1.1. be an experienced user of the Ekso device with a minimum of 20 hours and no more than 50 hours of device use and require no greater than minimal assist (support of up to 25% body weight) for safe and consistent walking.

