Physical Conditions	
 Temperature range 10-30 deg C Relative humidity range 20-95%, non-condensing Background sound pressure level: <70 dBA in the range of 100 Hz
Frequency of Use for Operator	
Maximum Frequency	6 hours per day

8. Recruitment Methods

8.1. Ekso Bionics will locate interested subjects from an existing group of prior test subjects. Additional networking for the purpose of identifying potential subjects will occur through rehabilitation hospitals currently using the Ekso Bionics device as well as non-for-profit organizations interested in supporting the individual use of Ekso. Since all recruitment will be verbal,

Protocol Name:	Investigational Study of the Ekso Bionics Powered Exoskeleton for High-Dosage Use by Individuals with Spinal Cord Injury in a Non-Clinical Environment
Principal Investigator:	[name], Sr. Controls Engineer
Primary Contact Name/Contact Info:	[name], Sr. Controls Engineer [contact] [contact]
Date Revised:	9/28/2015
Study Number:	13098-01

recruitment flyers or other marketing materials are not necessary. Hospitals acting as recruiting centers to locate Ekso Bionics test subjects may have their own IRB for recruiting only.

8.2. Ekso Bionics Clinical team members will perform the initial screening of potential participants. The team will determine study eligibility based on a clinical evaluation, home site evaluation, interviews with the prospective non-clinical spotter(s) and the experience and capability of the subject. They will discuss in detail the objectives, complete protocol, and its risks and potential benefits.

8.3. Once volunteers agree to participate they will be required to provide a medical release from their physician. Potential participants will read the Ekso Bionics informed consent and have an opportunity to ask questions and discuss the study with their physician, family, and friends before agreeing to enter the study. The informed consent and medical release (Appendix B) also include contact information should the participant or his/her associates have any questions. The original signed informed consent will be given to the participant, and a copy will be kept in a locked cabinet at Ekso Bionics accessible only by Investigators.

9. Number of Subjects

The study will consist of a minimum of two (2) subjects and a maximum of twelve (12).

10. Study Timelines

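### Protocol 14.8 tells researchers to ignore outliers by judgement and lets suspicious data be dropped unchecked, which can misstate the change and its spread in 2 to 12 subjects

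*Protocol*

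**What the plan says.** Section 14.8 gives two uses for the data: guiding development of the device for home use, and "to analyze the clinical effect on the subjects". It continues: "Much of the analysis will be subjective in nature where the researchers will ignore outliers", with data quality verified by eye. The next sentence reads: "Any suspicious data will be ignored or verified by comparing it with the videos and pictures".

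Other sections bear on how far this rule reaches:

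- Section 14.1: "Data may be collected manually, on video, on a computer embedded in the device or transferred to an Ekso Bionics computer". The data therefore include hand-recorded material as well as device output. Section 14.4 brings the section 6.1 measures (bowel, bladder, pain, quality of life and others) under the same heading.
- Section 9 sets the size at 2 to 12 subjects. No control group is described.
- The only timed mention of video is in section 6.6, where a follow-up evaluation "may be conducted either in-person or by video at weeks 3 and 7". Nothing schedules video or pictures of routine home sessions.

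No section defines an outlier or suspicious data, requires evidence of error before a value is ignored, requires exclusions to be logged, or asks for an analysis of all data.

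**The concern.** This is a rule the protocol lays down, not a detail left to a statistical analysis plan. An analysis plan that kept every genuine value would contradict it.

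Three features make the rule unsafe:

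- **Exclusion rests on judgement.** The criterion is how a value looks, not whether it is wrong.
- **Checking is optional.** Ignoring and verifying are offered as alternatives, and the only check named is against videos and pictures. Bowel, bladder, pain and quality-of-life forms could hardly be checked that way.
- **The unit is unstated.** An outlier could be a subject, a visit or a session reading.

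In so small a study one real non-responder, strong responder or worsened subject can be the outlier. Ignoring that subject understates variability and pulls the mean toward the majority, hiding a real harm or a real benefit. If exclusions lean one way, the apparent change is biased. The rule also permits, though it does not instruct, discounting a genuine safety observation.

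**Working it through.** The protocol gives no effect size, SD, test or cut-off, so there is no figure of its own to reproduce. The calculations below illustrate the consequence. From the document: n between 2 and 12 (section 9). Assumed: independent normal change scores with SD 1. The SD rules use each sample's own mean and SD; modified z means a cut-off of 3.5; boxplot means the 1.5 IQR rule. All act equally in both directions.

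**Step 1: can a cut-off flag anyone?** The largest possible standardised deviation in a sample of n is (n − 1)/√n.

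- n = 2: 1/√2 = 0.71
- n = 6: 5/√6 = 2.04
- n = 10: 9/√10 = 2.85
- n = 12: 11/√12 = 3.18

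A 3 SD rule can never flag a subject at n = 10 or below. At these sizes the unstated criterion decides whether anything counts as an outlier.

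**Step 2: one subject truly worsens by 3 SD and nobody else changes (400,000 replicates).** The true mean is −3/12 = −0.25 at n = 12 and −3/6 = −0.50 at n = 6.

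| Rule | Mean, n = 12 | Worsened subject dropped, n = 12 | Mean, n = 6 |
|---|---|---|---|
| Keep all | −0.25 | 0% | −0.50 |
| 3 SD | −0.249 | 0.2% | −0.500 |
| 2.5 SD | −0.178 | 21% | −0.500 |
| Modified z | −0.151 | 33% | −0.316 |
| Boxplot | −0.101 | 56% | −0.244 |
| 2 SD | −0.074 | 63% | −0.487 |

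At n = 12 the 2 SD rule hides (0.250 − 0.074)/0.250 = 70% of the true mean change. At n = 6 the boxplot rule hides (0.500 − 0.244)/0.500 = 51%. The average SD at n = 12 falls from 1.30 with all values to 1.00 under the 2 SD rule.

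**Step 3: no true effect.** This step assumes a one-sample t-test at two-sided 5%, which the protocol does not specify (400,000 replicates).

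| Rule | Rejections, n = 12 | Rejections, n = 6 |
|---|---|---|
| 3 SD | 4.96% | 4.91% |
| 2.5 SD | 5.73% | 4.91% |
| Modified z | 7.55% | 10.72% |
| 2 SD | 9.46% | 5.17% |
| Boxplot | 10.15% | 12.53% |

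These rules do not shift the mean. Two worst cases at n = 12:

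- Always dropping the lowest subject shifts the mean by +0.148 SD and rejects in 9.83% of runs (8.52% false benefit, 1.31% false harm).
- Always dropping the value farthest from the median rejects in 12.44% of runs, with no mean shift.

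**Step 4: single readings dropped instead of subjects.** Assume 52 independent normal readings per subject (200,000 replicates). Neutral removal leaves the subject's mean unshifted.

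| Rule | Ratio of reported to true within-subject SD | Mean shift if only low readings go (session SD) |
|---|---|---|
| 3 SD | 0.991 | +0.002 |
| 2.5 SD | 0.961 | +0.014 |
| 2 SD | 0.886 | +0.050 |

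Reported spread falls by 1% to 11%.

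**The case against.** The strongest reply is that 14.8 is about cleaning device data. It sits under data management, follows the list of device streams in 14.3, and names video as the comparator, which suits walking sessions and not questionnaires. On that reading the harm is that of Step 4, which is small. This limits the size of the concern but does not remove it. The text draws no such line, and 14.8 itself names clinical effect as a use of the data.

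The study is also an exploratory pilot with no stated hypothesis test, so the error rates in Step 3 attach to nothing in the protocol. That is right, and they are illustration only. Step 2 needs no test: the descriptive mean and spread, which are what a pilot reports, are themselves altered. It does rest on an assumed 3 SD worsening, and under some cut-offs almost nothing changes.

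Data are stored for ten years (14.5), and ignoring a value does not delete it. Re-analysis would be possible, but that does not correct a result already reported.

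The safety risk is limited by scheduled collection of secondary health conditions (6.1.8), three-monthly safety reviews (6.6), the stopping rule for adverse medical conditions (11.2.5), the daily log (12.2.8.2) and observation of physical and psychological deviations (12.3.8). These make the safety aspect secondary. None of them prevents a recorded value from being ignored in the analysis.

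**Conclusion.** The concern holds. Section 14.8 prescribes discretionary exclusion without a criterion, evidence of error or a compulsory check, for data that include clinical outcomes.

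The size depends on what is dropped. At subject level, with 12 subjects and one true 3 SD worsening, a true mean change of −0.25 SD could be reported almost in full or reduced to −0.07 SD. At reading level the effect is slight. These figures assume normal, independent scores and conventional cut-offs, none of which the protocol specifies. They show what the rule allows, not a bias that has been demonstrated. The wording should be corrected; it does not invalidate the study.

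**What to change.** Replace the outlier and suspicious-data sentences in 14.8 with:

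> No value is excluded because it is extreme. A value is corrected or set aside only when source records, video, pictures or the device log document a recording, transcription or sensor fault; each such decision and its reason are logged and listed. The main analysis uses all values except documented faults, and a sensitivity analysis includes all recorded values. Suspicious values that cannot be shown to be faulty are kept. Clinical and safety observations are never removed for being extreme.

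Section 14.9 needs no change. The cost is the protocol wording and a short exclusion log. Reported spread will be somewhat wider, and some undetected faulty readings will stay in the main analysis. The sensitivity analysis will include known faults, so a single corrupt device reading could dominate it; it should be read beside the main analysis and not in its place.
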